### **6.2.4 Double-blind End-of-Treatment Visits: Visit 4 (Day 57 -6) and Visit 5 (Day 57 ±3)**

The following will be performed/collected at Visit 4 (Day 57 – 6) or early withdrawal:

- estimated creatinine clearance
- clinical safety laboratory assessment: liver function tests (LFTs) and hematology
- Clinical Response Score (Table 2), based on subject recording of stool frequency and rectal bleeding in the daily diary
- flexible sigmoidoscopy/colonoscopy (at least 4 days prior to Visit 5 to allow sufficient time for the central reading)
- submit flexible sigmoidoscopy/colonoscopy recording to the independent central reader

The following will be performed/collected at Visit 5 (Day 57 ±3) or early withdrawal:

- physical examination, including weight
- vital signs (blood pressure and pulse rate)
- 12-lead ECG
- urine pregnancy testing (test strip) for females of childbearing age or <1 year postmenopausal; if positive, the subject will not be able to continue into the open-label period or Study 000175
- clinical safety laboratory assessment: chemistry, hematology, coagulation, standard urinalysis
- serum CRP and fecal calprotectin levels
- concomitant medication review
- calculation of Clinical and Endoscopic Response Score ([Table 2](#)).
- PGA
- calculation of Modified Mayo score
- IBDQ
- assessment of any AEs since the previous visit
- collection of trial medication
- review of subject daily diary data including compliance, and deactivation of subject daily diary for subjects not entering open-label period
- trial medication compliance assessment

At the end of Week 8, all subjects who do not meet the defined criteria for remission at Week 8 will be given an option to receive open-label treatment with mesalamine 4 g extended release granules (sachet) for 8 additional weeks in the current trial. IMP will be distributed and subjects will receive instructions on the administration of the trial medication. The first dose of IMP will be administered the day following the end of double-blind treatment visit. The IMP will be taken at least 1 hour before or at least 2 hours after a meal at approximately the same time each day during the open-label period.

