#### **6.2.6 Open-Label End-of-Treatment Visits: Visit 7 (Day 113 -6) and Visit 8 (Day 113 ±3)**

The following will be performed/collected at Visit 7 (Day 113 – 6) or early withdrawal:

- estimated creatinine clearance
- clinical safety laboratory assessment: liver function tests (LFTs) and hematology
- Clinical Response Score ([Table 2](#)), based on subject recording of stool frequency and rectal bleeding in the daily diary
- flexible sigmoidoscopy/colonoscopy (at least 4 days prior to Visit 8 to allow sufficient time for the central reading)
- submit flexible sigmoidoscopy/colonoscopy recording to the independent central reader

The following will be performed/collected at Visit 8 (Day 113 ±3) or early withdrawal:

- physical examination, including weight
- vital signs (blood pressure and pulse rate)
- 12-lead ECG
- urine pregnancy testing (test strip) for females of childbearing age or <1 year postmenopausal (if positive, the subject will not be enrolled in Study 000175)
- clinical safety laboratory assessment: chemistry, hematology, coagulation, standard urinalysis
- concomitant medication review
- serum CRP and fecal calprotectin levels
- calculation of Clinical and Endoscopic Response Score ([Table 2](#)).
- IBDQ
- assessment of any AEs since the previous visit
- collection of trial medication

- review of subject daily diary data including compliance, and deactivation of subject daily diary
- trial medication compliance assessment

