9.1 General Considerations

All statistical tests will be conducted at a two-sided 0.05 significance level.

Statistical tests for the primary and key secondary endpoints will be conducted using a fixed-sequence procedure according to the pre-specified order to maintain the overall Type I error rate to a two-sided 5%. All other secondary endpoints will be tested without adjustment for multiplicity.

Stool frequency and rectal bleeding scores at each visit will be calculated as an average of the daily scores collected within 5 days prior to the visit (excluding the visit day and the day before the visit day if the bowel preparation is needed on the day before the visit). If the daily scores in this period are available for fewer than 3 days, the average score will be considered missing. The average scores will be rounded to the nearest integer for the final score determination (e.g., 0.3 will be rounded to 0, and 0.5 will be rounded to 1).

The average scores will be calculated at Visit 2 (Week 2), Visit 3 (Week 4), and Visit 4 (Week 8) for the double-blind period, and Visit 6 (Week 10) and Visit 7 (Week 16) for the open-label period. Although both Visit 4 and Visit 5 are designated as Week 8 in the double-blind period, Visit 4 corresponds to the visit for the endoscopic assessment, and therefore, the stool frequency and rectal bleeding scores will be calculated at Visit 4. Similarly, the scores will be calculated at Visit 7 for the end of the open-label period instead of at Visit 8.

However, in one section (Section 7.1.3) of Protocol Amendment 2, it was unintentionally indicated that the scores would be calculated at Visit 5 and Visit 8 instead of Visit 4 and Visit 7. As a result, some of these subjects completed the diary fewer than 3 days within 5 days prior to Visit 4 and/or Visit 7 but completed 3 or more days prior to Visit 5 and/or Visit 8. Therefore, for those subjects who consented with Protocol Amendment 2, the average scores calculated at Visit 5 and/or Visit 8, as indicated in Section 7.1.3 of Protocol Amendment 2, will be used if the average scores at Visit 4 and/or Visit 7 are missing. Handling of other missing data in the statistical analyses will be described for each endpoint.

For the endoscopic assessment, the outcomes determined by the independent central reading procedure will be used for all analyses.

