For visit-based data, the data collected on the day that is closest to the scheduled trial day within a window will be assigned to the corresponding analysis visit. [Table 2](#) and [Table 3](#) show the scheduled trial day and window for each analysis visit during the double-blind period and open-label period, respectively.

Table 2 Scheduled trial day and window for analysis visits: double-blind period

Analysis visit	Scheduled trial day	Window
Baseline	Day 1	prior to the first dose of IMP

Week 2	Day 15	Day 1 to Day 22
Week 4	Day 29	Day 23 to Day 43
Week 8	Day 57	Day 44 or after, but before 1st dose of OL period

OL: open label

Table 3 Scheduled trial day and window for analysis visits: open-label period

Analysis visit	Scheduled trial day	Window
Week 10	Day 71	After 1st dose of OL period up to Day 92
Week 16	Day 113	Day 93 or after

OL: open label

If the closest day cannot be uniquely identified for an analysis visit, the data collected on an earlier trial day will be assigned to the analysis visit.

The efficacy data captured during the 8-week open-label period will be descriptively summarized and used for exploratory purposes only.

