9.2 Primary Endpoint(s)

9.2.1 Primary Variable(s) Analysis

The primary efficacy analysis will be based on all randomized subjects (ITT analysis set). The proportion of subjects with remission, defined as rectal bleeding score of 0 and stool frequency score of “0” or “1 with at least 1 point decrease from baseline” with an endoscopic score of 0 or 1 in the Clinical and Endoscopic Response Score at Week 8, will be compared between treatment groups using a chi-square test without a continuity correction at a two-sided 0.05 significance level. Subjects who discontinue the double blind regimen before Week 8, as well as subjects with missing remission assessment at Week 8, will be considered not having achieved remission. The odds ratio for the treatment group compared to the control group will be estimated and its 95% confidence interval will be provided using the Woolf’s approximation (Woolf, 1955)(6).

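### Should the Amendment 2 fallback to the Visit 5 diary score leave out the bowel-preparation day before Visit 4?

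*SAP*

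**What the plan says.** SAP 9.1 averages the daily scores from the 5 days before a visit, "excluding the visit day and the day before the visit day if the bowel preparation is needed on the day before the visit". With fewer than 3 days available the average is missing. "The average scores will be rounded to the nearest integer for the final score determination", and 0.5 goes up to 1. Week 8 is scored at Visit 4 because the endoscopy is done there.

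SAP 9.1 then explains that Section 7.1.3 of Amendment 2 named Visits 5 and 8 by mistake. Some subjects therefore had too few diary days before Visit 4 or 7 but "completed 3 or more days prior to Visit 5 and/or Visit 8". For subjects who consented under that amendment, "the average scores calculated at Visit 5 and/or Visit 8, as indicated in Section 7.1.3 of Protocol Amendment 2, will be used" when the Visit 4 or Visit 7 average is missing.

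Protocol 6.2.4 places Visit 4 at Day 57 (-6) and Visit 5 at Day 57 (±3), and lists for Visit 4 "flexible sigmoidoscopy/colonoscopy (at least 4 days prior to Visit 5 to allow sufficient time for the central reading". Protocol 6.2.6 sets the same spacing for the open-label period: "flexible sigmoidoscopy/colonoscopy (at least 4 days prior to Visit 8 to allow sufficient time for the central reading". No endoscopy is scheduled at Visit 5 or Visit 8. The current Protocol 7.1.3 has a plain five-day rule and mentions no preparation day for any visit.

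Under SAP 9.2.1, "subjects with missing remission assessment at Week 8, will be considered not having achieved remission". For the open-label data, SAP 9.1 says: "The efficacy data captured during the 8-week open-label period will be descriptively summarized and used for exploratory purposes only".

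**The concern.** The SAP treats a diary entry made on a preparation day as unfit for the Week 8 score. When the score moves from Visit 4 to Visit 5, however, the exclusion moves with it and looks only at the day before Visit 5, when no preparation is scheduled. If the two visits are close enough, the preparation day before Visit 4 falls inside the Visit 5 window.

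Take a subject who needs preparation and makes entries on days -5, -4 and -1 relative to Visit 4. Day -1 is rejected, two entries remain, and the Visit 4 score is missing. At a 4-day gap the fallback then accepts that same day -1 entry.

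The Week 8 scores decide the primary endpoint and the first key secondary endpoint. One entry could therefore change a subject's remission status, and in either direction.

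**Working it through.** **The plan's own figure.** The only design figure stated is at least 85% power with 110 per group, 36% against 18%, two-sided 0.05. Check: z = [√110 × 0.18 − 1.96 × √(2 × 0.27 × 0.73)] / √(0.36 × 0.64 + 0.18 × 0.82) = (1.888 − 1.231) / 0.615 = 1.07, which gives 85.7%. It reproduces, and nothing below depends on it.

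**Day count.** Let Visit 4 be day 0 and the preparation day be -1. With a gap of g days, the Visit 5 window runs from g − 5 to g − 1. Visit 4 may fall on Days 51–57 and Visit 5 on Days 54–60, with g at least 4.

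| Gap | Allowed day pairs | Window relative to Visit 4 | Preparation day inside? | Visit 4 day inside? |
|---|---|---|---|---|
| 4 | 6 | -1 to +3 | yes | yes |
| 5 | 5 | 0 to +4 | no | yes |
| 6 to 9 | 4 + 3 + 2 + 1 = 10 | +1 or later | no | no |

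The preparation day is inside for 6 of 21 pairs. With Visit 5 on Day 57, that is one of the three allowed Visit 4 days (Day 53). The Visit 4 day, which SAP 9.1 also excludes from the Visit 4 score, is inside for 6 + 5 = 11 of 21 pairs. These are counts of allowed pairs, not frequencies. Visits 7 and 8 give the same counts.

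**Diary patterns at a 4-day gap.** The score exists with 3 or more of 5 entries: 10 + 5 + 1 = 16 patterns. The preparation day is entered in those with at least 2 of the 4 other days: 6 + 4 + 1 = 11. In 4 + 1 = 5 of these, three or more other entries exist. In the other 6, the preparation-day entry is needed to reach the minimum.

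**Can the entry change the result?** Yes, with assumed scores and a baseline stool score of 2 or more:
- Stool 1, 1, 1 averages 1.0 and passes. Adding a 3 gives 6/4 = 1.5, which rounds to 2 and fails.
- Stool 2, 2, 1 averages 1.67, rounds to 2 and fails. Adding a 0 gives 5/4 = 1.25, which rounds to 1 and passes.
- Bleeding 1, 1, 0, 0 averages 0.5, rounds to 1 and fails. Adding a 0 gives 2/5 = 0.4, which rounds to 0 and passes.

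Over all combinations of scores 0 to 3, the entry changes the component result as follows:

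| Component | Other entries | Pass to fail | Fail to pass | Combinations | Share changed |
|---|---|---|---|---|---|
| Stool | 3 | 34 | 12 | 256 | 18% |
| Stool | 4 | 40 | 128 | 1,024 | 16% |
| Bleeding | 3 | 11 | 0 | 256 | 4% |
| Bleeding | 4 | 9 | 10 | 1,024 | 2% |

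These shares weight every combination equally and are not estimates of how often subjects change.

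**Size.** The documents give none of the rates needed, so all of these are assumptions: 30–100% of the 220 subjects consented under Amendment 2; 3–20% of those on the fallback; 30% at a 4-day gap; half needing preparation the day before; 70% making an entry that day; 12% of those entries changing remission status.
- Subjects whose preparation-day entry counts: low 220 × 0.30 × 0.03 × 0.30 × 0.5 × 0.7 = 0.21; high 220 × 1.00 × 0.20 × 0.30 × 0.5 × 0.7 = 4.6.
- Status changed by it: × 0.12 = 0.025 to 0.55.
- Changed back by a rule that drops the day only if three other entries remain: × 5/11 = 0.01 to 0.25.

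Even if every fallback subject were at a 4-day gap, the upper figure would be 0.252 / 0.30 = 0.84 of a subject, both arms together.

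**The case for a change.** The best argument for a change is consistency. The SAP has judged preparation-day entries unsuitable, the derivation feeds the primary endpoint, and some subjects did lack the Visit 4 diary days, so the fallback will be used. One sentence could drop the preparation day whenever three other entries remain and flag the rest. All 16 patterns would stay scorable, so no one would return to missing.

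The inconsistency stands; the remedy does not repay it. It corrects 5 of the 11 affected patterns and still counts the preparation day in the other 6. It also adds a third rule: for Visit 4 the SAP drops the day even if the score becomes missing, whereas here exclusion would depend on how complete the diary is. It leaves the Visit 4 day in the window at gaps of 4 and 5 days, which covers more allowed pairs than the preparation day does.

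A strict exclusion would be cleaner but would make those 6 patterns missing, which SAP 9.2.1 counts as non-remission. That works against a fallback meant to avoid penalising subjects for following the amendment they signed. Dropping the Visit 4 day as well would leave only days +1 to +3 at a 4-day gap, exactly the three-entry minimum.

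Nor is a discretionary programming choice left open. Read literally, SAP 9.1 gives one answer: the five days before Visit 5, with no preparation day to remove. That may be deliberate, since the fallback is defined by what Amendment 2 told sites to do, and the current Protocol 7.1.3 has no preparation-day exclusion either. Amendment 2's own text is not available, so one cannot say that it lacks such an exclusion, only that SAP 9.1 states none that reaches this day.

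**Conclusion.** No change is needed. The overlap is real but confined to the minimum 4-day gap. To matter, it needs a subject consented under Amendment 2, a missing Visit 4 average, at least three entries before Visit 5, preparation on the day before Visit 4, an entry that day, and a rounded score that crosses the cut-off with every other remission criterion met. On the assumed inputs, the partial remedy would alter remission status for about 0.01 to 0.25 subjects in the whole trial. The rule is the same in both arms and the change can go either way, so no effect on type I error or power is claimed. The Visit 7 and 8 part touches exploratory open-label summaries only.

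This is a fair trade-off: the fallback keeps subjects evaluable at the price of an occasional preparation-day entry. The size rests on assumed rates. A fallback share well above 20%, or text in Amendment 2 that sets a different window, would be the reason to look again.

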9.2 Primary Endpoint(s)

9.2.1 Primary Variable(s) Analysis

The primary efficacy analysis will be based on all randomized subjects (ITT analysis set). The proportion of subjects with remission, defined as rectal bleeding score of 0 and stool frequency score of “0” or “1 with at least 1 point decrease from baseline” with an endoscopic score of 0 or 1 in the Clinical and Endoscopic Response Score at Week 8, will be compared between treatment groups using a chi-square test without a continuity correction at a two-sided 0.05 significance level. Subjects who discontinue the double blind regimen before Week 8, as well as subjects with missing remission assessment at Week 8, will be considered not having achieved remission. The odds ratio for the treatment group compared to the control group will be estimated and its 95% confidence interval will be provided using the Woolf’s approximation (Woolf, 1955)(6).

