### **9.6.2 Primary Endpoint**

The primary efficacy analysis will be based on all randomized subjects (ITT analysis set). The proportion of subjects with remission, defined as rectal bleeding score of 0 and stool frequency score of 0 or 1 with at least 1 point decrease from baseline, with an endoscopic score of 0 or 1 in the Clinical and Endoscopic Response Score at Week 8, will be compared between treatment groups using the chi-square test at a two-sided 0.05 significance level. Subjects who discontinue the double-blind regimen before Week 8, as well as subjects with missing remission assessment at Week 8, will be considered not having achieved remission. The odds ratio will be estimated and its 95% confidence interval will be provided.

The following sensitivity analyses will be conducted to assess the robustness of the primary analysis:

- As-treated analysis based on actually received treatment
- Analysis on the mITT analysis set
- Analysis on the PP analysis set
- Assessment of the homogeneity of odds ratios across geographical regions, baseline demographic characteristics, and baseline disease characteristics
- Analysis on the last observed Clinical and Endoscopic Response Score
- Analysis using multiple imputation methods for missing remission assessment at Week 8
- Analysis using pattern mixture models for missing remission assessment at Week 8

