3.2 Determination of Sample Size

The true remission rates at Week 8 for mesalamine 4 g extended-release granules (sachet) and placebo regimens were assumed as 36% and 18%, respectively, based on Kamm et al. (2007)(3), Lichtenstein et al. (2007)(4), and Marteau et al. (2005)(5). Under these assumptions, a sample size of 110 randomized subjects per group will provide at least 85% power to detect a statistically significant treatment group difference in the remission rate at a two-sided 0.05 significance level using the chi-square test.

4 Subject Disposition

The number of screened subjects will be summarized, and for subjects not randomized, the primary reason for exclusion from randomization will be summarized.

The number and percentage of subjects who are randomized, are treated with IMP, prematurely discontinued, and completed the double-blind period of the trial will be summarized with the reason of premature discontinuations. Similar summaries will be made for subjects who are enrolled to the 8-week open-label period.

The time to discontinuation will be summarized by the Kaplan-Meier estimates, and the treatment group difference will be tested by the log-rank test. In addition, reason-specific discontinuation will be summarized by the cumulative incidence estimates.

5 Protocol Deviations

The following protocol deviations will be identified as major protocol deviations:

- Overall IMP compliance of less than 80% during the double-blind period
- Not taking the randomized IMP
- Taking prohibited medications during the double-blind period

The final definition of major protocol deviations will be determined prior to breaking the blind.

The number and percentage of subjects with protocol deviations will be summarized.

6 Analysis sets

For each analysis set, the number and percentage of subjects excluded from it will be summarized by the reason of the exclusion.

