9.2.2 Sensitivity Analyses

The following sensitivity analyses will be conducted to assess the robustness of the primary analysis:

- As-treated analysis based on actually received treatment
- Analysis on the mITT analysis set
- Analysis on the PP analysis set
- Analysis using the last observed Clinical and Endoscopic Response Score
- Fisher-exact test combined with Cornfield’s exact 95% CI (Cornfield, 1956)(7)

The same analysis conducted for the primary analysis will be repeated for these sensitivity analyses.

Since the definition of remission was modified during the study, an analysis based on the original definition, i.e., rectal bleeding and stool frequency scores of 0 with an endoscopic score of 0 or 1 in the Clinical and Endoscopic Response Score, will also be conducted for reporting purpose.

In addition, sensitivity analyses using multiple imputation (MI) methods and pattern mixture models (PMMs) under missing at random (MAR) and missing not at random (MNAR) assumptions, respectively, will be conducted.

Under the MAR assumption, the missing stool frequency and rectal bleeding scores (Clinical Response scores) for Weeks 2, 4, and 8 will be imputed sequentially by regression-based imputation models using treatment group, baseline characteristics, and outcomes from preceding visits as the predictors. Once the missing Week 8 Clinical Response scores have been imputed, Week 8 Endoscopic Response score will be imputed by regression-based imputation models using treatment group, baseline characteristics, and Week 8 Clinical Response scores as the predictors. Based on the imputed Clinical and Endoscopic Response scores, the remission status at Week 8 will be determined. This imputation procedure will be repeated 100 times, and the primary analysis method will be applied to each of the imputed dataset. A combined estimate of the odds ratio for the treatment group compared to the control group and its 95% confidence interval will be obtained by the methods described in Rubin (1987)(8).

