Under the MNAR assumption, a similar MI method described above will be applied. However, in this analysis, only the data from the control group will be used for the regression-based imputation for Clinical Response scores at each visit and Endoscopic Response score at Week 8 by assuming that subjects from the treatment group will follow the same profile as the subjects on the control group after withdrawal from the study (Little & Yau, 1996(9); Ratitch & O’Kelly, 2011(10)).

The primary endpoint will also be analyzed for the following subgroups for the ITT analysis set. The homogeneity of odds ratios across the strata will be tested by the Breslow-Day test at a 0.05 significance level, and the odds ratios for each subgroup will be presented in forest plots.

- Baseline demographic characteristics (age, gender, and race)
- Baseline disease characteristics (previous 5-ASA treatment (yes/no), extent of UC, and severity of UC)
- Geographical region (North America including US and Canada or rest of the world)

The treatment group comparisons after controlling each factor listed above will be conducted by the Mantel-Haenszel test as sensitivity analyses.

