9.3 Secondary Endpoint(s)

9.3.1 Key Secondary Endpoints

The following key secondary endpoints will be analyzed for the ITT analysis set.

1. The proportion of subjects with remission in the primary endpoint and the PGA score of ≤ 1 (Modified Mayo) at Week 8
2. Time to cessation of rectal bleeding, defined as time in days from randomization to the first day of 3 consecutive days with a rectal bleeding score of 0, based on subject daily diary

If the primary efficacy analysis demonstrates a statistically significant difference between the treatment groups, the first key secondary endpoint will be compared using the same statistical method used for the primary efficacy analysis. Only if the analysis for the first key secondary endpoint is statistically significant at a two-sided 0.05 significance level, the second key secondary endpoint will be declared statistically significant when the log-rank test is statistically significant at a two-sided 0.05 significance level. The hazard ratio of cessation of rectal bleeding for mesalamine relative to placebo will be estimated (including the 95% CI) using the Cox proportional hazards model with treatment group as a factor.

For the first key secondary endpoint, subjects who discontinue the double blind regimen before Week 8, as well as subjects with missing assessment at Week 8, will be considered not having achieved the response criteria.

For the second key secondary endpoint, if a subject does not achieve the cessation of rectal bleeding by Day 56, the time to cessation of rectal bleeding will be censored at the earlier of the day that the last diary entry is made or Day 56.

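### Does the plan need an ITT analysis that counts subjects who took prohibited UC therapy as non-remitters?

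*SAP*

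**What the plan says.** Protocol 9.6.2 and SAP 9.2.1 analyse all randomized subjects and impute non-remission by two routes. The SAP's wording is "Subjects who discontinue the double blind regimen before Week 8, as well as subjects with missing remission assessment at Week 8", and the Protocol's matches it. For key secondary 1, SAP 9.3.1 has "subjects who discontinue the double blind regimen before Week 8, as well as subjects with missing assessment at Week 8". Use of other UC drugs is not a route.

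Protocol 4.3.2 bans non-trial 5-ASA, corticosteroids, immunomodulators and biologics, and also antidiarrheals and some other drugs. Protocol 3.5.7 and 4.4 withdraw a subject whose UC worsens and needs escalated therapy; beyond the listed cases, withdrawal is left to the investigator or the subject.

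SAP section 5 lists "Taking prohibited medications during the double-blind period" as a major deviation. SAP 6.3 removes subjects with major deviations from the per-protocol (PP) set, and SAP 9.2.2 plans "Analysis on the PP analysis set" for the primary endpoint. Protocol 9.4 and SAP section 6 report exclusions from each set by reason. SAP 7.3 tabulates concomitant drugs by ATC class and treatment group. Protocol 9.6.1 lists all data by subject and visit.

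**The concern.** A subject may enter on oral 5-ASA at 2.5 g/day or less (Protocol 4.1.2), keep taking it against the ban, stay on trial product and meet the Week 8 criteria. Continuing is not an increase in dose, so the escalation criterion in Protocol 4.4 does not clearly apply. That subject is an ITT remitter.

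The other analyses in SAP 9.2.2 do not isolate such subjects. The mITT, last-observed-score, Fisher and original-definition analyses leave them as they are. The as-treated analysis has no stated rule for prohibited drugs. Multiple imputation and the pattern-mixture model act on gaps in the data ("the missing stool frequency and rectal bleeding scores (Clinical Response scores) for Weeks 2, 4, and 8 will be imputed sequentially"), and these subjects have scores. The 5-ASA subgroup is defined by previous use. The PP set reacts, but it also drops subjects with compliance below 80% or not taking the randomized product, and it is no longer a fully randomized comparison. Key secondary 1 has no sensitivity analysis.

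Near the boundary one subject can matter: 33 against 20 remitters of 110 is significant, 32 against 20 is not.

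**Working it through.** **1. The plan's own figure.** Inputs from SAP 3.2: n = 110 per arm, 36% against 18%, two-sided 0.05, chi-square; no continuity correction (SAP 9.2.1).

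Power = Φ[(d − 1.96·s0)/s1], with s0 = √(2p̄(1−p̄)/n) and s1 = √([p1(1−p1)+p2(1−p2)]/n). With p̄ = 0.27, s0 = 0.0599 and s1 = 0.0586, so power = Φ[(0.18 − 0.1173)/0.0586] = Φ(1.07) = 85.7%. The stated figure of at least 85% reproduces.

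**2. Dilution under the present rule.** Usage rates are assumptions, since the documents give none. The gain per user is taken as 9 or 18 percentage points; 18 is the plan's own mesalamine effect and so an upper value. Observed rate = base rate + use × gain.

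| Use, placebo / mesalamine | Gain | Mesalamine vs placebo | Power |
|---|---|---|---|
| none | – | 0.3600 vs 0.1800 | 85.7% |
| 5% / 2% | 9 points | 0.3618 vs 0.1845 | 84.4% |
| 5% / 2% | 18 points | 0.3636 vs 0.1890 | 83.0% |
| 10% / 4% | 9 points | 0.3636 vs 0.1890 | 83.0% |
| 10% / 4% | 18 points | 0.3672 vs 0.1980 | 80.0% |

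**3. How many reclassified remitters change the conclusion.** With equal arms, χ² = 220(a−b)²/[(a+b)(220−a−b)].

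- 40 vs 20: 220·400/(60·160) = 9.17, p = 0.0025.
- 33 vs 20: 220·169/(53·167) = 4.20, p = 0.040.
- 32 vs 20: 220·144/(52·168) = 3.63, p = 0.057.
- 32 vs 19: 220·169/(51·169) = 4.31, p = 0.038.

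From the planned rates, 8 mesalamine remitters must be lost with none on placebo (40 to 32). The 33-to-32 example also reclassifies nobody on placebo. With one remitter reclassified per arm, 33 vs 20 becomes 32 vs 19 and stays significant.

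Exact binomial enumeration at 36% and 18% gives the chance that a significant trial loses significance: 3.5%, 7.4% and 11.9% if 1, 2 or 3 mesalamine remitters and no placebo remitters are reclassified, but effectively zero for one per arm, or for one mesalamine and two placebo.

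**4. What the assumed usage implies.** At 5% / 2%, users number 110 × 0.05 = 5.5 on placebo and 110 × 0.02 = 2.2 on mesalamine. Remitting users (no gain to 18-point gain) are 5.5 × 0.18 = 1.0 to 5.5 × 0.36 = 2.0 on placebo, and 2.2 × 0.36 = 0.8 to 2.2 × 0.54 = 1.2 on mesalamine. That is the pattern with essentially no loss of significance. Losing 8 mesalamine remitters takes 8/0.54 = 15 to 8/0.36 = 22 users in that arm.

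**5. False positives with no drug effect (18% in both arms).** Exact chance of a significant result favouring mesalamine; nominal 2.50%. The present rule uses an 18-point gain. Counting users as failures multiplies the base rate by (1 − use).

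| Use, placebo / mesalamine | Present rule | Users as failures |
|---|---|---|
| 5% / 2% | 0.1836 vs 0.1890: 1.95% | 0.1764 vs 0.1710: 3.20% |
| 10% / 4% | 0.1872 vs 0.1980: 1.52% | 0.1728 vs 0.1620: 4.08% |
| 0% / 5% | 0.1890 vs 0.1800: 3.67% | 0.1710 vs 0.1800: 1.65% |

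(Rates are mesalamine vs placebo. With a 9-point gain at 5% / 2% the present rule gives 2.21%.)

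If use is higher on placebo, the present rule is the more conservative one. The order reverses if use is confined to mesalamine.

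**The case for a change.** The best case for a change is that PP cannot stand in for an ITT reclassification. Starting from 40 vs 20, reclassifying 8 mesalamine remitters gives p = 0.057. Dropping the same 8, as PP would, gives 32/102 vs 20/110: χ² = 212·(32·90 − 70·20)²/(102·110·52·160) = 4.97, p = 0.026. The two can disagree. The analysis would also be cheap: the drug data are collected, major deviations are settled before unblinding, and SAP 9.2.2 already adds an analysis ("Fisher-exact test combined with" exact limits) that Protocol 9.6.2 does not list. A drug list chosen after unblinding would be open to challenge.

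The disagreement between the two methods stands, but that example needs 8 remitting users on mesalamine and none on placebo. The objection that PP mixes several deviations stands only in part: exclusions are counted by reason, and the listings let a reader look up the outcomes of those excluded for prohibited drugs.

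Key secondary 1 adds little, because each of its responders is by definition a primary remitter, and the plan lists no sensitivity analyses for any secondary endpoint.

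Nor is the obvious version of the analysis clean. Restricted to 5-ASA, corticosteroids, immunomodulators and biologics, it would omit antidiarrheals, which bear on stool frequency. Without an indication limit it would fail a subject given a steroid for another reason. It would also need separate windows, since diary scores and endoscopy belong to Visit 4 and the PGA to Visit 5.

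**Conclusion.** No change follows. It is true that no ITT analysis counts users of prohibited therapy as non-remitters. But the primary rule is a legitimate, defined choice, and the plan already covers most of the issue through withdrawal for escalation, medication review at Visits 2, 3 and 5, the PP analysis and exclusions reported by reason.

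The residual group is probably small, though the documents give no rate to confirm it. Under the assumed 5% / 2% use the cost is 1.3 to 2.7 points of power (85.7% to 84.4% or 83.0%), in the conservative direction. The conclusion would weaken if use were concentrated among mesalamine remitters, a pattern nothing in the documents suggests.

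A sponsor could add a supportive analysis outside the fixed sequence, with the drug list, indications and windows fixed while blinded. That is a fair trade-off to decline: it would usually confirm the result, and it leans toward mesalamine when placebo subjects use more of these drugs.
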